7.2 Statistical Methods

Statistical analyses will utilize an Intention to Treat (ITT) approach. Mixed models analyses with growth curve estimates will form the basis of the core analyses.

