This material is the property of the University of Minnesota. Do not disclose or use except as authorized in writing by the study sponsor

CONFIDENTIAL

This material is the property of the University of Minnesota. Do not disclose or use except as authorized in writing by the study sponsor

8.6	MEDICAL MONITORING	22
8.6.1	Internal Data and Safety Monitoring Board	23
8.6.2	Independent Data and Safety Monitoring Board	23
9	DATA HANDLING AND RECORD KEEPING	23
9.1	CONFIDENTIALITY	23
9.2	SOURCE DOCUMENTS	24
9.3	CASE REPORT FORMS	24
9.4	RECORDS RETENTION	24
10	STUDY MONITORING, AUDITING, AND INSPECTING	25
10.1	STUDY MONITORING PLAN	25
10.2	AUDITING AND INSPECTING	25
11	ETHICAL CONSIDERATIONS	25
12	STUDY FINANCES	26
12.1	FUNDING SOURCE	26
12.2	CONFLICT OF INTEREST	26
12.3	SUBJECT STIPENDS OR PAYMENTS	26
13	PUBLICATION PLAN	26
14	REFERENCES	26
15	ATTACHMENTS	33

CONFIDENTIAL

This material is the property of the University of Minnesota. Do not disclose or use except as authorized in writing by the study sponsor

List of Abbreviations

CFR	Code of Federal Regulations
CNBD	Center for Neurobehavioral Development
CRF	Case Report Form
FAS	Fetal Alcohol Syndrome
FASD	Fetal Alcohol Spectrum Disorders
FDA	Food and Drug Administration
GCP	Good Clinical Practice
GRAS	Generally Recognized as Safe
ICH	International Conference on Harmonization
IRB	Institutional Review Board
RDI	Recommended Dietary Intake

CONFIDENTIAL

This material is the property of the University of Minnesota. Do not disclose or use except as authorized in writing by the study sponsor

Study Summary

Title	Choline Supplementation as a Neurodevelopmental Intervention in Fetal Alcohol Spectrum Disorders
Short Title	Choline supplementation in FASD.
Protocol Number	1R01AA024123
Phase	Phase I and II
Methodology	Randomized, double-blind, placebo-controlled
Study Duration	Five years
Study Center(s)	Single-center
Objectives	To evaluate the feasibility and tolerability of post-natal choline supplementation in young children
Number of Subjects	60
Diagnosis and Main Inclusion Criteria	Fetal alcohol spectrum disorder; documented prenatal alcohol exposure
Study Product, Dose, Route, Regimen	Choline bitartrate, 19 mg per kg body weight (typical range: 200-425 mg; max dose 500 mg), oral solution administered once daily
Duration of administration	Nine months
Reference therapy	Placebo
Statistical Methodology	Mixed models growth curve analyses of the outcome measures using and Intention to Treat (ITT) approach

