3.1 General Design

This is a randomized, double-blind, placebo-controlled study. Sixty children, male and female, between the ages of 2 years and 5 years at enrollment will be included.

Eligible participants will be randomized to treatment or placebo in a 1:1 allocation ratio. A block randomization procedure with variable block sizes will be used to maximize unpredictability of assignment.

Participants will receive the test article for nine months and will have an in-person baseline visit followed by 11 additional visits (9 telephone visits; 2 additional in-person visits) for a total of 12 visits. A telephone visit for purposes of safety and compliance will occur at 2 weeks. A telephone visit will be scheduled for 1 month after administration of the test article begins. Formal complete follow-up assessments will occur at 6 months and 9 months. Telephone visits for safety and compliance will occur at months 2, 3, 4, 5, 7, 8 and 10. Parent-report measures of behavior will be collected. Behavioral paradigms will be used to assess memory and other cognitive functions. Formal psychometric testing to establish developmental levels will be completed. Blood will be collected to assess compliance with the treatment and effect on blood choline levels. DNA will also be extracted for analysis of single nucleotide polymorphisms related to endogenous choline production. Plasma will also be analyzed for immune function and micro-RNA.

As part of the project, participants from the previous study (1R21AA019580 / 4R33AA019580) will be brought back to the University for a set of cognitive evaluations to assess the long-term effects of having taken choline/placebo previously.

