3.2 Primary Study Endpoints

The primary study endpoints will be cognitive assessments. These will include the Elicited Imitation memory task and the Stanford-Binet Intelligence Scales.

CONFIDENTIAL

This material is the property of the University of Minnesota. Do not disclose or use except as authorized in writing by the study sponsor

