6.1 Visits 1, 8, & 11 (Baseline and follow-up assessment visits)

Participants and their parent/guardians identified as described in Section 4.3 of this protocol will be asked to come for a baseline visit (Visit 1). This visit is expected to last for approximately 3 to 3.5 hours. Visits 8 and 11 will be similar, but slightly shorter (2.5 to 3 hours) because several tasks are not repeated. The following procedures will occur:

- Consenting process (Visit 1 only);
- Medical history (Visit 1 only) and physical exam
- Concomitant medications will be recorded
- Height
- Weight
- Head circumference
- Facial photograph to allow for detailed measurements (Visit 1 only)
- Blood pressure
- Blood collection for choline and metabolite (betaine, phosphatidylcholine, sphingomyelin, and trimethylamine-N-oxide (TMAO) level (3 ml tube).
- Plasma extracted from this whole blood will be analyzed for measures of immune function (cytokines) and micro-RNA..
- Extraction of DNA sample from any blood sample for single nucleotide polymorphisms related to endogenous choline synthesis (PEMT rs12325817)
- Astley & Clarren's FASD diagnostic evaluation including a photograph of the child's face for computer measurement and analysis (Visit 1 or Visit3)
- Stanford Binet Intelligence Scales, Fifth Edition (Visit 1 and 11 only)
- Elicited Imitation Paradigm, including video-recording to facilitate scoring afterward
- Minnesota EF Scale (MEFS), Early Childhood Version
- NIH Toolbox Flanker Inhibitory Control and Attention Task
- Beery Developmental Test of Visual-Motor Integration (VMI) (any visit)
- Scales of Independent Behavior (SIB) (any visit)
- Child behavioral questionnaires (CBCL); a parent-report instrument
- 24-hour Diet interview (for the parent/guardian to complete about the subject)
- Child Eating Behavior Questionnaire (CEBQ); a parent-report instrument
- Randomization (Visit 1 only)
- Training on how to store, mix, and administer the study medication (Visit 1 only)
- Adverse events will be recorded (Visits 8 & 11 only)
- Dispense a supply of the test article (30 packages at Visit 1)
- Provide instructions for returning for the next follow-up visit (Visits 1 & 8 only)

6.2 Visits 2, 3, 4, 5, 6, 7, 9, 10 & 12 (compliance/safety phonecontacts)

At each of these visits, study staff will place a phone call to the participant's parent/guardian. The following information will be collected:

CONFIDENTIAL

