7.1 Sample Size Determination

For purposes of sample size determination, the dependent measure was the percent of correct items on delayed recall of the EI task (averaged across two events per timepoint). The effect size from our completed trial was $d=0.66$. A power analysis was carried out using Optimal Design Software for Multi-level and Longitudinal Research (Version 3.01) to determine the sample size that would be necessary to detect a difference in linear change between treatment and placebo groups with this effect size (Feingold 2009). The analysis assumed that the data would be analyzed using a mixed models repeated measures design for a person-randomized trial, with an effect size $d=.66$, and a two-tailed type I error of 0.05. To achieve 80% power, a sample size of 58.5 participants (approximately 30 per treatment arm) is necessary. This is consistent with the significant group difference that was observed in the pilot trial. The sample size for the proposed study will therefore be fixed at 60 children. Combining participant data

CONFIDENTIAL

This material is the property of the University of Minnesota. Do not disclose or use except as authorized in writing by the study sponsor

for some outcome measures from the first set of pilot studies (N=60) and the proposed study (N=60) will provide additional power to further evaluate age, sex, and PEMT genotype as moderating variables.

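### Section 7.2 does not say how the Visit 1 score enters the growth-curve model; if the arms have separate intercepts, the analysis is valid but usually gives up some precision on both primary endpoints

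*Combined protocol and SAP*

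**What the plan says.** Section 7.2 has two sentences. One adopts intention to treat; the other reads "Mixed models analyses with growth curve estimates will form the basis of the core analyses". The Study Summary agrees: "Mixed models growth curve analyses of the outcome measures". Section 7.1 sizes the trial on delayed recall in Elicited Imitation, to "detect a difference in linear change between treatment and placebo groups" with d=0.66 and a two-tailed 0.05 test: "To achieve 80% power, a sample size of 58.5 participants (approximately 30 per treatment arm) is necessary". N is then fixed at 60.

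The design facts that bear on the model are these.

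- Section 3.1: "Eligible participants will be randomized to treatment or placebo in a 1:1 allocation ratio", and "Formal complete follow-up assessments will occur at 6 months and 9 months".
- Section 3.2, on the primary endpoints: "These will include the Elicited Imitation memory task and the Stanford-Binet Intelligence Scales".
- Section 6.1: Elicited Imitation carries no visit restriction in the list for Visits 1, 8 and 11, so it falls at months 0, 6 and 9. The other endpoint is restricted: "Stanford Binet Intelligence Scales, Fifth Edition (Visit 1 and 11 only".
- Section 6.1 also places randomisation at Visit 1, the visit of the baseline tests.

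Nothing says whether the arms share an intercept, whether baseline is an outcome or a covariate, how time is coded, or which covariance is fitted.

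**The concern.** A growth-curve contrast of linear change is commonly fitted with an arm main effect plus arm-by-time. The arm main effect estimates a baseline difference that randomisation makes zero in expectation, and estimating it usually costs precision. For Stanford-Binet, with two visits, the growth curve then reduces to comparing mean change scores.

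Elicited Imitation is sized with almost no margin (58.5 needed, 60 planned, no stated dropout allowance), so precision matters there. Section 7.1 does not size the trial on Stanford-Binet, so nothing is known about its margin. For both endpoints, stating the baseline handling would also fix the form of the primary comparison before data are seen.

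**Working it through.** **Inputs from the documents:** d=0.66, two-sided 0.05, 80% power at N=58.5, N=60 at 1:1 (30 per arm), visits at 0, 6 and 9 months. **Assumed:** all correlations and variance components, d in baseline-SD units, complete data, and d=0.5 for Stanford-Binet.

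**The plan's own figure.** 58.5 cannot be rerun from the printed inputs, because the variance components are not given. A plain two-sided comparison of two means at d=0.66 needs 37 per arm (74 in total). A one-sided t-test needs 58.2 in total, but section 7.1 says two-tailed. A separate-intercept linear growth model under compound symmetry gives 58.5 at rho of about 0.59. So 58.5 is unverifiable, not shown wrong; below it only calibrates an illustration.

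**Stanford-Binet (two visits, SD=1 at both).**
- Change score: variance of the arm difference = 4(1-rho)/30, which is 0.0533 at rho 0.6 and 0.0267 at 0.8.
- Baseline-adjusted: 2(1-rho²)/30, which is 0.0427 and 0.0240.
- Ratio = (1+rho)/2, which is 0.80 and 0.90.
- Power at d=0.5 (noncentral t, 58 and 57 df): 57% to 66% at rho 0.6; 85% to 89% at 0.8. Simulation with the baseline slope estimated gave 56% to 65% and 85% to 88%, with type I error 0.051 for both methods. The gain disappears above rho of about 0.97.
- Unequal SDs, with k = Visit 11 SD / Visit 1 SD: ratio = k²(1-rho²)/(1+k²-2·rho·k). At rho 0.6 this is 0.60 for k=0.8, 0.80 for k=1 and 0.96 for k=1.3. It equals 1 when rho·k=1.

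**Elicited Imitation (t = 0, 6/9, 1), compound symmetry, rho=0.593.** Sum of t = 1.667; sum of t² = 1.444.
- Separate intercepts: variance = 2(1-rho)/(30 × [1.444 - 1.667²/3]) = 0.813/(30 × 0.5185) = 0.0523.
- Common baseline mean: variance = 2(1-rho)/(30 × [1.444 - 1.667²·rho/(1+2·rho)]) = 0.813/(30 × 0.691) = 0.0392.
- Ratio 0.75; power at N=60 goes from 81% to 91%.

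**Elicited Imitation, random slopes.** Slope variance is 0.1, 0.2 or 0.3 of baseline variance, with intercept variance re-solved (0.645, 0.697, 0.749) so that 58.5 still gives 80%. Separate intercepts give 81% throughout. A common baseline with the same linear contrast gives:

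| Intercept-slope correlation | 0.1 | 0.2 | 0.3 |
|---|---|---|---|
| -0.3 | 91% | 91% | 90% |
| 0 | 88% | 86% | 85% |
| +0.3 | 86% | 83% | 82% |
| +0.5 | 84% | 82% | 81% |

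**Wrong covariance.** Suppose slopes vary but only a random intercept is fitted (intercept variance 0.7, residual 0.3, large-sample calculation).
- Slope variance 0.2, correlation +0.3: type I error is 0.067 with separate intercepts and 0.089 with a shared baseline.
- Slope variance 0.3, correlation +0.5: 0.074 and 0.109. Here the shared-baseline estimate also has about 3% more true variance.

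**Effect not linear in time (rho 0.593).** An effect of 0.66 appearing only at month 9 is estimated as 0.566 with separate intercepts and 0.523 with a shared baseline. One already complete at month 6 is estimated as 0.707 and 0.728.

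**The case against.** The strongest reply is that the loss is hypothetical: the text is silent, and the sponsor's model may already share or adjust for baseline. That stands, and the point is conditional for this reason. Section 7.2 still needs the sentence, because the primary contrast is otherwise open.

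Second, this is a matter of efficiency. The separate-intercept model is valid and matches the contrast powered in section 7.1. That also stands; no error of validity is claimed.

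Third, the size rests on assumed quantities, and 81% to 91% depends on a correlation back-solved from a figure that cannot be verified. This stands in full. The figure is one illustration, and other plausible settings give almost no gain.

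Fourth, sharing the baseline is not automatically safe. The type I error figures above bear this out, so the covariance must be part of the change. Lower variance is assured only when the covariance is correctly modelled.

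Fifth, section 6.4 says that missing cognitive scores are common in such studies, and plain ANCOVA drops children who lack either score. This stands too, and favours the mixed-model form for Stanford-Binet.

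**Conclusion.** The concern holds in conditional form. Sections 7.1 and 7.2 state no use of the randomised baseline. With separate intercepts the planned analysis is valid and usually less precise than an analysis of the same data that uses it. For Stanford-Binet the variance reduction is 20% at rho 0.6 and 10% at 0.8 with equal SDs. It is smaller if the Visit 11 SD is larger, and vanishes as rho times the SD ratio nears 1. For Elicited Imitation it is about 0 to 10 power points over the settings examined.

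A reader might infer that the plan does fit separate intercepts, that both primary endpoints therefore lose precision, or that the trial forgoes 10 points of power. The documents do not support this: they fix neither the intercepts nor the covariance. Nor do they support calling the planned analysis biased. Confidence is firm on direction under a correctly modelled covariance, and low on size. The change is worth making because it needs no new data.

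**What to change.** In section 7.2, state for each primary endpoint how baseline is handled.

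- **Stanford-Binet:** a two-visit mixed model with a common baseline mean and unstructured covariance, which keeps children with only one score. ANCOVA of the Visit 11 score on the Visit 1 score is the complete-data equivalent.
- **Elicited Imitation delayed recall (months 0, 6, 9):** keep the linear arm-by-time contrast, drop the arm main effect, and specify an unstructured covariance (or random intercept and slope) with small-sample degrees of freedom. Do not rely on a random intercept alone.
- State that baseline testing at Visit 1 precedes the first dose, which the common mean requires. Section 6.1 lists testing, randomisation and training together without giving an order.

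If the sponsor's model already does this, only the wording changes. The cost is text and model code, with no new visit, measure or child. The downsides are a few more covariance parameters at N=60, and somewhat different weighting of months 6 and 9 from the separate-intercept model if the effect is not linear in time.

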7.3 Subject Population(s) for Analysis

Not applicable

8. Safety and Adverse Events

8.1 Definitions

8.1.1 Adverse Event

An **adverse event** (AE) is any symptom, sign, illness or experience that develops or worsens in severity during the course of the study. Intercurrent illnesses or injuries should be regarded as adverse events. Abnormal results of diagnostic procedures are considered to be adverse events if the abnormality:

- results in study withdrawal
- is associated with a serious adverse event
- is associated with clinical signs or symptoms
- leads to additional treatment or to further diagnostic tests
- is considered by the investigator to be of clinical significance

8.1.2 Serious Adverse Event

Adverse events are classified as serious or non-serious. A **serious adverse event** is any AE that is:

- fatal
- life-threatening
- requires or prolongs hospital stay
- results in persistent or significant disability or incapacity
- a congenital anomaly or birth defect
- an important medical event

Important medical events are those that may not be immediately life threatening, but are clearly of major clinical significance. They may jeopardize the subject, and may require intervention to prevent one of the other serious outcomes noted above. For example, drug overdose or abuse, a seizure that did not result in in-patient hospitalization, or intensive treatment of bronchospasm in an emergency department would typically be considered serious.

All adverse events that do not meet any of the criteria for serious should be regarded as **non-serious adverse events**.

8.1.3 Adverse Event Reporting Period

CONFIDENTIAL

This material is the property of the University of Minnesota. Do not disclose or use except as authorized in writing by the study sponsor

The study period during which adverse events must be reported is normally defined as the period from the initiation of any study procedures to the end of the study treatment follow-up (10 months in the case of this study).

8.1.4 Preexisting Condition

A preexisting condition is one that is present at the start of the study. A preexisting condition should be recorded as an adverse event if the frequency, intensity, or the character of the condition worsens during the study period.

8.1.5 General Physical Examination Findings

At screening, any clinically significant abnormality should be recorded as a preexisting condition. At the end of the study, any new clinically significant findings/abnormalities that meet the definition of an adverse event must also be recorded and documented as an adverse event.

8.1.6 Post-study Adverse Event

All unresolved adverse events should be followed by the investigator until the events are resolved, the subject is lost to follow-up, or the adverse event is otherwise explained. At the last scheduled visit, the investigator will instruct each subject to report any subsequent event(s) that the subject, or the subject's personal physician, believes might reasonably be related to participation in this study.

8.1.7 Abnormal Laboratory Values

A clinical laboratory abnormality will be documented as an adverse event if any one of the following conditions is met:

- The laboratory abnormality is not otherwise refuted by a repeat test to confirm the abnormality
- The abnormality suggests a disease and/or organ toxicity
- The abnormality is of a degree that requires active management; e.g. change of dose, discontinuation of the drug, more frequent follow-up assessments, further diagnostic investigation, etc.

8.1.8 Hospitalization, Prolonged Hospitalization or Surgery

Any adverse event that results in hospitalization or prolonged hospitalization will be documented and reported as a serious adverse event unless specifically instructed otherwise in this protocol. Any condition responsible for surgery will be documented as an adverse event if the condition meets the criteria for an adverse event.

Neither the condition, hospitalization, prolonged hospitalization, nor surgery are reported as an adverse event in the following circumstances:

- Hospitalization or prolonged hospitalization for diagnostic or elective surgical procedures for a preexisting condition. Surgery should **not** be reported as an outcome of an adverse event if the purpose of the surgery was elective or diagnostic and the outcome was uneventful.

CONFIDENTIAL

This material is the property of the University of Minnesota. Do not disclose or use except as authorized in writing by the study sponsor

- Hospitalization or prolonged hospitalization required to allow efficacy measurement for the study.
- Hospitalization or prolonged hospitalization for therapy of the target disease of the study, unless it is a worsening or increase in frequency of hospital admissions as judged by the clinical investigator.

8.2 Recording of Adverse Events

At each contact with the participant family, the investigator will seek information about adverse events through specific questioning. At each in-person visit, the investigators will also directly evaluate for adverse events by examination. Information on all adverse events will be recorded immediately in the source document, and also in the appropriate adverse event module of the case report form (CRF). Clearly related signs, symptoms, and abnormal diagnostic procedures results will be recorded in the source document.

All adverse events occurring during the study period will be recorded. The clinical course of each event will be followed until resolution, stabilization, or until it has been determined that the study treatment or participation is not the cause. Serious adverse events that are still ongoing at the end of the study period will be followed up to determine the final outcome. Any serious adverse event that occurs after the study period and is considered to be possibly related to the study treatment or study participation will be recorded and reported immediately.

8.3 Reporting of Serious Adverse Events

8.3.1 Study Sponsor Notification by Investigator

A serious adverse event will be reported to the IRB and to the study sponsor (NIH) by telephone within 24 hours of the event. A Serious Adverse Event (SAE) form will be completed by the investigator and faxed to the IRB and to the study sponsor within 24 hours. The investigator will keep a copy of this SAE form on file at the study site.

Report serious adverse events by phone and facsimile to:

[name].

Voice: [contact]

[contact]

[contact]

[contact]

At the time of the initial report, the following information will be provided:

- Study identifier
- Study Center
- Subject number
- A description of the event
- Date of onset
- Current status
- Whether study treatment was discontinued
- The reason why the event is classified as serious
- Investigator assessment of the association between the event and study treatment

CONFIDENTIAL

This material is the property of the University of Minnesota. Do not disclose or use except as authorized in writing by the study sponsor

Within the following 48 hours, the investigator will provide further information on the serious adverse event in the form of a written narrative. This will include a copy of the completed Serious Adverse Event form, and any other diagnostic information that will assist the understanding of the event. Significant new information on ongoing serious adverse events will be provided promptly to the study sponsor

